2.9 RISKS AND BENEFITS

Potential risks associated with infusion of MSCs include a reaction to the product (rash, shortness of breath, coughing, wheezing, difficulty breathing, hypotension, hypertension, hypoxia, swelling around the mouth, throat or eyes, tachycardia, bradycardia, diaphoresis), transmission of infection, and HLA sensitization. Theoretical risks that must be considered but have not been associated with MSC administration in humans include the possibility of immune suppression and ectopic tissue formation. Cord blood collected with the cord tissue used to manufacture hCT-MSC is screened for infection, and the product must meet release criteria prior to infusion, as described below. Participants will not receive immunosuppressive therapy prior to or after infusion of hCT-MSC cells. Additionally, an inherent risk in completing study procedures in person is possible exposure to COVID-19; however, social distancing, screening, masking, cleaning and other safety procedures in line with the most recent guidelines from Duke Health and the Duke University School of Medicine have been implemented to minimize this risk as much as is feasible.

Potential benefits of this intervention include the possibility that hCT-MSC may, via direct or indirect mechanisms, induce changes that result in the reduction of the participant's core ASD symptomatology and improvement in abilities affected by ASD symptoms.

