4.2 STUDY FLOW CHART

4.3 STUDY ENDPOINTS

Safety Endpoints:

Safety of hCT-MSC infusion in children with ASD will be assessed by:

- 1. Incidence and severity of infusion reactions
- 2. Incidence and severity of product-related infections
- 3. Evidence of alloimmunization via anti-HLA antibodies
- 4. Incidence and severity of graft vs. host disease
- 5. Incidence and severity of unexpected adverse events, by relation to study product

Efficacy Endpoints:

The primary clinical outcome measure is the change in social communication abilities from baseline to 6 months based on total score (1-7) on the Joint Engagement Rating Inventory (JERI), a commonly-used and well-validated coding system for rating the quality and quantity of social communication skills in toddlers with and without ASD.⁹¹

Change measured on the following endpoints from baseline to six months will be compared:

- 1. PDD Behavior Inventory Autism Composite Score (PDDBI)
- 2. Mean of the Socialization Subscale and Communication Subscale standard scores on the Vineland Adaptive Behavior Scales (VABS-3)
- 3. Clinical Global Impression Scale (CGI) Severity and Improvement (Improvement at 6 months only

4. Communicative Development Inventories (CDI-2): Words & Sentences subscales

Exploratory Endpoints:

Change measured from baseline to six months will be evaluated on the following outcome measures.

- 1. Changes in auditory orienting, facial expressions, look duration, attention to social and nonsocial stimuli, postural sway, and vocalizations as measured via computer vision analysis by an app that elicits and records autism symptoms on an iPad (SenseToKnow)
- 2. PDD Behavior Inventory (PDDBI) Subscales
- 3. VABS-3 Socialization Subscale Standard Score and age equivalent
- 4. VABS-3 Communication Subscale Standard Score and age equivalent
- 5. VABS-3 Daily Living Subscale Standard Score and age equivalent
- 6. VABS-3 Adaptive Behavior Composite Standard Score and age equivalent
- 7. Pediatric Quality of Life Scale Generic Core

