5.3 EXCLUSION CRITERIA

- 1. General:
 - a. Review of medical records indicates ASD diagnosis not likely
 - b. Screening data suggests that participant would not be able to comply with the requirements of the study procedures as assessed by the study team
 - c. Family is unwilling or unable to commit to participation in all study-related assessments, including protocol follow up
 - d. Sibling is enrolled in this (Duke TACT) study
- 2. Genetic:
 - Records indicate that child has a known genetic syndrome such as (but not limited to) Fragile X syndrome, neurofibromatosis, Rett syndrome, tuberous sclerosis, PTEN mutation, cystic fibrosis, muscular dystrophy or a genetic mutation known to be associated with ASD

- b. Known pathogenic mutation or copy number variation (CNV) associated with ASD (e.g., 16p11.2, 15q13.2, 2q13.3)
- 3. Infectious:
 - a. Known active CNS infection
 - b. Evidence of uncontrolled infection based on records or clinical assessment
 - c. Known HIV positivity
 - d. Exposure to COVID-19 in the preceding 14 days or positive COVID-19 test in the previous 28 days. Subjects with a past history of infection with COVID-19 must be symptom-free for 14 days prior to the initial visit

4. Medical:

- a. Known metabolic disorder
- b. Known mitochondrial dysfunction
- c. History of unstable epilepsy or uncontrolled seizure disorder, infantile spasms, Lennox Gastaut syndrome, Dravet syndrome, or other similar chronic seizure disorder
- d. Active malignancy or prior malignancy that was treated with chemotherapy
- e. History of a primary immunodeficiency disorder
- f. History of autoimmune cytopenias (i.e., ITP, AIHA)
- g. Coexisting medical condition that would place the child at increased risk for complications of study procedures
- h. Concurrent genetic or acquired disease or comorbidity(ies) that could require a future stem cell transplant
- i. Significant sensory (e.g., blindness, deafness, uncorrected hearing impairment) or motor (e.g., cerebral palsy) impairment
- j. Impaired renal or liver function as determined by serum creatinine >1.5mg/dL or total bilirubin >1.3mg/dL, except in patients with known Gilbert's disease
- k. Significant hematologic abnormalities defined as: Hemoglobin <10.0 g/dL, WBC < 3,000 cells/mL, ALC <1000/uL, Platelets <150 x 10e9/uL
- I. Known clinically relevant physical dysmorphology associated with neurodevelopmental conditions.
- 5. Current/Prior Therapy:
 - a. History of prior cell therapy

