8.5 PRIMARY ENDPOINTS

The primary outcome is safety. Safety endpoints will include the incidence of infusion reactions, infections, and new-onset clinically significant anti-HLA antibodies. Presence of infusion reactions and infections will be assessed in person at the time of infusion, 24 hours after infusion, and at six months and will be assessed remotely at 7-10 days post-infusion and 12 months and will be reported descriptively. Anti-HLA antibodies will be assessed at six and 12 months post-infusion.

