9.2 ADVERSE EVENT REPORTING

All adverse events reported or observed during the study beginning at the time of the initial infusion must be recorded. AEs occurring in 5% of enrolled participants will be reported in clinicaltrials.gov. Information to be reported includes date when the site became aware of the event, investigator-specified assessment of severity and relationship to study therapy, whether there is an alternative etiology, seriousness, as well as any required treatment or evaluations, and

outcome. In general, investigators should report adverse events as diseases or syndromes whenever possible, instead of reporting individual component symptoms, signs, laboratory abnormalities, and sequelae.

Severe adverse infusion reactions (fatal, life-threatening or requiring hospitalization) will be reported within seven calendar days of receipt of the information. All fatal or life threatening SAEs will be reported by the investigator or its representatives to the FDA by telephone or fax within seven calendar days after receipt of the information, following FDA guidelines. All serious and unexpected AEs will be reported to the FDA via a written report within 15 days of receipt of the information (21 CFR 312.32). If the principal investigator assesses an event to be unrelated to the study, then the event will not require expedited reporting but will be included in the annual summary report.

The following events within 24 hours of hCT-MSC infusion will also be recorded in the e-CRF: infusion reaction, sinus bradycardia, sinus tachycardia, hypertension, hypotension, fever, rigors/chills, nausea, vomiting, infection, dyspnea, hypoxia, and hemoglobinuria.

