9.4 ELICITING ADVERSE EVENT INFORMATION

In addition to research participant observations, AEs will be documented from any data collected throughout the study including clinically significant laboratory values or physical exam findings.

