28	Has your child ever had any problems with involuntary movements?				
29	Is your child chronically tired or fatigued?				
30	Has your child ever had cancer?				
31	Has your child ever had a tumor?				
32	Has your child ever had any unexplained masses or growths?				
33	Have you ever had any other concerns about your child's medical health? If so, please explain below.				
34	Has your child ever had any significant problems sleeping at night?				
35	Has your child ever had any significant problems being too sleepy during the day?				
36	Has your child ever had differences in sensory processing such as sensory seeking behaviors or sensory aversion behaviors (including food aversion)?				
37	Has your child ever had any problems with rituals, being flexible, repetitive behaviors or repetitive language?				
38	Has your child ever had any problems with hyperactivity or impulsivity?				
39	Has your child ever had any significant problems with refusing to follow directions that he/she understands?				
40	Has your child ever had any significant problems with aggression, irritability or getting frustrated easily?				
41	Has your child ever had significant problems (more frequent/severe than other kids) with meltdowns or agitation?				
42	Has your child ever had any problems with staying motivated?				
43	Has your child ever had ever any problems with worries or sadness?				
44	Has your child ever had any problems with hurting him/herself on purpose or wanting to die?				
45	Has your child ever had any significant problems with mood swings?				
46	Has your child ever had any problems with believing things that aren't true or seeing/hearing things that aren't there?				
47	Has your child ever had any problems with seeming not to know where he/she was or what was really happening?				
48	Have you ever had any other concerns about your child's behavior, which is not addressed in questions 33-45? If so, please explain below.				

Please use the space below to explain any "yes" answers.

FOLLOW-UP MEDICAL & BEHAVIORAL HISTORY QUESTIONNAIRE

Please tell us if your child has ever experienced any significant problems with any of the following conditions SINCE YOU LAST COMPLETED THIS QUESTIONNAIRE.

		Pas mor	
		No	Yes
1	Has your child had any fevers?		
2	Has your child had infections?		
3	Has your child had any allergic reactions?		
4	Has your child had any new or worse problems with autoimmune disorders?		
5	Has your child had any new rashes or abnormal skin lesions?		

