6	Has your child developed jaundice (yellowing of the skin or eyes)?		
7	Has your child received a blood transfusion?		
8	Has your child had any new problems with bloody noses, easy bruising or prolonged bleeding?		
9	Has your child had any abnormal blood tests since their last visit?		
10	Has your child had any new or worsening problems with breathing, asthma or coughing?		
11	Has your child had any new or worsening problems with their heart?		
12	Has your child had any new problems with his/her mouth or teeth? (Do not include losing baby teeth.)		
13	Has your child had any new or worsening bowel problems, including bowel accidents?		
14	Has your child had any new or worsening diarrhea?		
15	Has your child had any new or worsening episodes of vomiting?		
16	Has your child had any new or worsening problems with appetite?		
17	Has your child had any new or worsening problems with weight?		
18	Has your child had any new or worsening problems with his/her muscles or joints?		
19	Has your child had any new or worsening swelling in any part of his or her body?		
20	Has your child had any new or worsening problems when he/she urinates?		
21	Has your child had any new or worsening problems with his/her breasts/nipples or private parts?		
22	Has your child had any changes in thirstiness?		
23	Has your child had any new or worsening problems with his/her ears or hearing?		
24	Has your child had any new or worsening eye or vision problems?		
25	Has your child had any new or worsening headaches?		
26	Has your child had any new or worsening problems with dizziness?		
27	Has your child had any new or worsening seizures?		
28	Has your child had any new or worsening problems with involuntary movements?		
29	Has your child had any new or worsening chronic tiredness or fatigue?		

		Pas	st 3
		mor	nths
		No	Yes
30	Has your child ever had cancer?		
31	Has your child ever had a tumor?		
32	Has your child ever had any unexplained masses or growths?		
33	Has your child been hospitalized? If so, please explain below.		
34	Has your child had any new significant injuries?		
35	Have you ever had any other concerns about your child's medical health? If so, please explain below.		
36	Has your child had any new or worsening problems sleeping at night?		
37	Has your child had any new or worsening problems being too sleepy during the day?		

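### Four follow-up safety items, including those on cancer, tumor and masses, ask *ever* on a form that covers only the time since the last questionnaire, so a yes can be old or new

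*Combined protocol and SAP*

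**What the plan says.** Section 2.9 lists theoretical risks that have to be considered although they have not been associated with these cells in humans. They "include the possibility of immune suppression and ectopic tissue formation".

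Section 6.6 gives the Appendix 1 questionnaire the task of assessing for serious adverse events. Section 7.5.3 and the table in 7.6.2 schedule it at baseline and at 3, 6, 9 and 12 months. The follow-up version asks about "any of the following conditions SINCE YOU LAST COMPLETED THIS QUESTIONNAIRE", under a past-3-months column. Item 32 of that version asks: "Has your child ever had any unexplained masses or growths". Items 30 (cancer), 31 (tumor) and 35 (other medical concerns) also use *ever*.

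The primary safety list in section 8.5 reads: "Safety endpoints will include the incidence of infusion reactions, infections, and new-onset clinically significant anti-HLA antibodies". Section 4.3 adds graft versus host disease and a general item, "Incidence and severity of unexpected adverse events, by relation to study product". Neither list names growths, tumors or ectopic tissue. On general capture, section 9.2 says: "All adverse events reported or observed during the study beginning at the time of the initial infusion must be recorded". Section 9.4 says: "AEs will be documented from any data collected throughout the study including clinically significant laboratory values or physical exam findings".

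On eligibility, exclusion 4d in section 5.3 removes children with "Active malignancy or prior malignancy that was treated with chemotherapy".

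**The concern.** A follow-up safety form should separate what happened after treatment from what was there before. For cancer, tumor and unexplained masses, the items closest to the ectopic tissue risk in section 2.9, the question and the form's instruction point different ways. A parent who follows the question answers for the child's lifetime. A parent who follows the instruction answers for about three months. The tick does not show which was done.

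Two errors become possible. A growth that predates the infusion can appear as a follow-up yes. And in a child who already had one, a further growth after infusion produces the same yes as before. With 12 children and purely descriptive reporting, a single ambiguous answer matters to anyone reading the safety data.

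**Working it through.** The plan states no figure that depends on this point, and section 8.4 gives no alpha, power or effect size, so there is nothing to reproduce. The check is a comparison of wording, with a little arithmetic for scale.

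1. **Item count on the follow-up form.** It has 51 items. Those that say *new*, *worse* or *worsening* number 39. Eight more ask about the interval without those words and without *ever*: items 1, 2, 3, 6, 7, 9, 22 and 33. Four ask *ever*: 30, 31, 32 and 35. Check: 39 + 8 + 4 = 51, so 47 items do not ask *ever*.

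2. **Match with baseline.** Follow-up items 30 to 32 repeat baseline items 30 to 32 word for word, and follow-up item 35 repeats baseline item 33. On the baseline form *ever* is right, because there is an EVER column beside a past-2-months column. The follow-up form has only the recent column. The four items look like carry-over.

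3. **Can an affected child enrol?** Exclusion 4d covers active malignancy and malignancy treated with chemotherapy. A benign growth, or a tumor treated another way, is not removed by 4d. Other exclusions, such as the genetic ones, may remove some of these children. The documents give no rate.

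4. **What else could separate old from new?**
   - The baseline form holds the earlier answer.
   - Both forms ask for an explanation of any yes.
   - The schedule in 7.6.1 has a history and physical at baseline and 6 months, but not at 12 months, when section 7.1 makes the safety assessment remote.
   - Sections 9.2 and 9.4 give general adverse event capture from the infusion onward.
   - No section says that a follow-up yes must be compared with the baseline answer, or how a yes becomes an adverse event.

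5. **Scale, for illustration only.** Assume one child has a pre-existing growth and the parent answers *ever* literally each time.
   - Follow-up forms: 12 children × 4 = 48, of which 4 would be positive for that child.
   - If that child were wrongly counted as a new case: 1/12 = 8.3%, exact (Clopper-Pearson) 95% interval 0.2% to 38.5%.
   - The correct count would be 0/12, with two-sided upper limit 1 − 0.025^(1/12) = 26.5%.
   - Two such children would give 2/12 = 16.7% (2.1% to 48.4%).

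   These figures need the assumed child, the literal reading and a tabulation of ticks as incidence. The plan contains no such tabulation.

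**The case against.** The strongest reply is that the form corrects itself. The instruction uses *ever* inside a limited window and the column repeats that window, so a careful parent would answer for the interval. The baseline form already records earlier growths, and any yes has to be explained. Item 32 asks only about unexplained masses, so a diagnosed benign growth need not be ticked there. Follow-up item 19 (new or worsening swelling), item 5 (new skin lesions) and item 33 (hospitalization) offer other routes to a new growth. The risk is theoretical on the protocol's own account: section 2.4 cites 2434 doses of another such product, mostly in its paediatric GvHD experience, without ectopic tissue formation.

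Most of this stands, and it limits the harm. It does not remove the contradiction. Relying on parents to let the instruction override the question, and on staff to notice from free text, is weaker than asking the right question.

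A reader might go further and infer that the trial has no safety endpoint that would count a new growth. The documents do not support that. Such an event, once recognised, falls under the fifth safety endpoint in 4.3 and the recording rules in 9.2 and 9.4; what is missing is a named line for it. A reader might also infer that a pre-infusion growth will be recorded as a follow-up event. That is not established either: nothing turns a questionnaire tick into an adverse event, and 9.2 starts the recording window at the initial infusion.

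**Conclusion.** The point holds as a defect in a data-collection form. Follow-up items 30, 31, 32 and 35 contradict the form's instruction, its column and its other 47 items. A growth present before infusion could be reported again, and in that child the tick alone would not reveal a new one.

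The effect on results is limited. No planned figure changes, and general adverse event capture remains in place. The 1/12 and 2/12 incidences show only what a miscount would look like in a sample of 12; they rest on an assumed number of affected children for which the documents give no basis. The correction is still worth making. These answers bear on a risk that section 2.9 names, they sit on the form used to look for serious adverse events, and after the 6-month visit no further physical examination is scheduled to help interpret them.

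**What to change.** - Reword follow-up items 30 to 32 to ask whether, since the last questionnaire, the child has had a new cancer, tumor, or unexplained mass or growth, or whether an existing one has enlarged.
- Reword follow-up item 35 to ask about any other new or worsening medical concerns.
- Add one sentence to section 6.6 or 9.4: any yes on these items is compared with the baseline answer before it is recorded as an adverse event. The same comparison can be applied to follow-up forms already completed.

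The cost is the wording of four items and one sentence, with the IRB review that section 12.3 requires for any change. No visit, procedure or analysis is added.

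Optionally, list children with new or enlarging masses as a descriptive line (n/12) in the safety table. For a theoretical risk in a study of this size that is a matter of preference, and the rewording does not depend on it.

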38	Has your child had any new or worsening problems with differences in sensory processing such as sensory seeking behaviors or sensory aversion behaviors (including food aversion)?		
39	Has your child had any new or worsening problems with rituals, being flexible, repetitive behaviors or repetitive language?		
40	Has your child had any new problems with hyperactivity or impulsivity?		
41	Has your child had any new or worsening problems with refusing to follow directions that he/she understands?		
42	Has your child had any new or worsening problems with aggression, irritability or getting frustrated easily?		
43	Has your child had any new or worsening with meltdowns or agitation?		
44	Has your child had any new or worsening problems with staying motivated?		
45	Has your child had any new or worsening problems with worries or sadness?		
46	Has your child had any new or worsening problems with hurting him/herself or wanting to die?		
47	Has your child had any new or worsening problems with mood swings?		
48	Has your child had any new or worsening problems with believing things that aren't true or seeing/hearing things that aren't there?		
49	Has your child had any new or worsening problems with knowing where he/she is or who is with him/her?		
50	Has your child had any new or worsening problems with their thinking?		
51	Have there been any other new or worsening problems with your child's behavior, which is not addressed in questions 35-50? If so, please explain below.		

Please use the space below to explain any "yes" answers.

Open Label Phase I HCT-MSC in Toddlers with ASD (TACT)

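### Follow-up safety item 40 asks only about new hyperactivity or impulsivity, so the form can miss a worsening in a child who already had it

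*Combined protocol and SAP*

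**What the plan says.** Appendix 1 holds a baseline and a follow-up version of the medical and behavioural history questionnaire. Section 6.6 schedules the Appendix 1 form at each later visit and at 3, 9 and 12 months. Section 7.5.3 and the table in Section 7.6.2 place it at baseline, 3, 6, 9 and 12 months.

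At baseline, item 38 asks "Has your child ever had any problems with hyperactivity or impulsivity". At follow-up, item 40 on the same topic asks "Has your child had any new problems with hyperactivity or impulsivity". The items on either side are worded more widely. Item 39 asks "Has your child had any new or worsening problems with rituals, being flexible, repetitive behaviors or repetitive language" and item 41 asks "Has your child had any new or worsening problems with refusing to follow directions that he/she understands". The behavioural section closes with item 51: "Have there been any other new or worsening problems with your child's behavior, which is not addressed in questions 35-50".

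Three medical items are also limited to new problems: item 5 (rashes and skin lesions), item 8 ("Has your child had any new problems with bloody noses, easy bruising or prolonged bleeding") and item 12 (mouth or teeth).

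Section 9.2 states: "All adverse events reported or observed during the study beginning at the time of the initial infusion must be recorded". It does not limit adverse events to conditions with new onset.

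**The concern.** The form treats worsening of an existing behaviour as something to report, and does so for every specific behavioural topic except this one. Because the baseline form asks about hyperactivity and impulsivity, some enrolled children can be expected to have them already. For those children, item 40 read literally calls for a no even after a clear deterioration.

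Objective 1 is safety and tolerability, and Section 4.3 lists unexpected adverse events by relation to study product as a safety endpoint. Section 9.2 can capture only what is reported or observed. Wording that discourages a report can lower the count but cannot raise it, so any error favours the product. With 12 children and no control arm, a single case matters to the descriptive safety table.

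**Working it through.** The plan gives no figure on this point, so the check is a reading of the form item by item.

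**Count of the behavioural items (follow-up form, 36 to 50).**
- Number of specific items: 50 − 36 + 1 = 15.
- Items asking about new or worsening problems: 36 to 39 (4 items) and 41 to 50 (10 items), so 4 + 10 = 14.
- Items asking about new problems only: item 40, so 15 − 14 = 1.

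**Path of one answer.** Take a child whose parent answered yes to baseline item 38 and whose hyperactivity becomes worse by month 3.
1. Item 40 asks about new problems. The problem is not new, so no is a truthful answer.
2. Item 51 does ask about worsening, but only for behaviour outside items 35 to 50. Item 40 lies inside that range. A parent who reads the range by topic will answer no again.
3. The free-text box is there to explain yes answers, so two no answers leave nothing to explain.

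**Other scheduled sources.**

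| Source | Timing | Would it catch this? |
|---|---|---|
| Instruction line above the follow-up form | Each completion | Possibly. It refers to any significant problem since the last form, but the yes or no is recorded against each item's own wording |
| Staff contact (6.6) | 7-10 days | Yes, for the first days only |
| History and physical (7.6.1) | Baseline and 6 months | Possibly, at 6 months |
| CGI parent interview (7.5.2, 7.6.2) | Baseline and 6 months | Possibly, at 6 months |
| PDDBI (7.5.3) | Every three months | Unclear. It rates problem behaviours, but the protocol does not say it covers hyperactivity and gives no rule for turning a score change into an adverse event |
| Any data collected (9.4) | Throughout | Only if some other source has recorded it |

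The table in Section 7.6.1 has no column for 3 or 9 months. Section 2.8 mentions a remote safety assessment at three months but names no instrument for it. The Appendix 1 questionnaire is therefore the only safety instrument named at those two points.

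**What one child means.** One case among 12 is 1/12 = 8.3%. Section 9.2 sets 5% of enrolled participants as the level for reporting on the public registry. One missed child can therefore decide whether an event type appears there.

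**The case against.** Several points on the other side are sound.

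**Worsening is not wholly unasked.** A reader might infer that it is never asked about. The documents do not support that. The instruction line is not limited to new onset, and the 7-10 day contact, the 6-month visit and Section 9.4 are all open to it.

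**Item 51 is ambiguous rather than closed.** Item 40 addresses only new problems, so a parent could take a worsening as not yet addressed and report it under item 51. The exclusion is one reasonable reading, not the only one.

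**The predecessor study does not show the gap in action.** Section 2.6 reports 22 psychiatric or behavioural symptoms apart from agitation during the infusion procedure, and it is tempting to cite them as the events at risk. The itemised list sums to 22 (2 + 5 + 3 + 2 + 1 + 1 + 3 + 1 + 4), and none is hyperactivity or impulsivity. The documents do not say which form that study used, so the zero does not prove absence either.

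**The loss cannot be sized from the documents.** Suppose 3 to 9 of the 12 children were affected at baseline and each had a 5% to 20% chance of worsening. The form would then miss at most 0.05 × 3 = 0.15 to 0.20 × 9 = 1.8 expected cases. Both inputs are assumptions, and the sum supposes that no affected child is picked up by item 51 or any other route. It should not be cited as a result.

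**The reach is limited.** Section 6.6 gives the form's purpose as assessing serious adverse events, and hospitalisation has its own item (33). This weakens the point but does not remove it: the form asks about many non-serious matters, and Section 9.2 wants all adverse events recorded.

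**Items 5, 8 and 12 are a lesser matter.** Item 51 is not their catch-all. Item 35, an open question on other medical concerns, gives them an outlet.

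**Conclusion.** The gap is real but modest. Item 40 is the one specific behavioural item out of 15 that omits worsening, and nothing in the protocol suggests the omission is deliberate. No item explicitly asks about worsening of existing hyperactivity or impulsivity, and item 51 can be read as excluding it. The result may be under-ascertainment of one kind of behavioural adverse event, in the direction of no harm, chiefly at 3 and 9 months.

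This rests on two assumptions: that some enrolled children have hyperactivity or impulsivity at baseline, and that some parents answer each item as worded. The documents quantify neither, so no number of lost events is claimed. The primary safety outcomes in Sections 4.1 and 8.5 do not depend on item 40. What is touched is the unexpected adverse event endpoint in Section 4.3 and the descriptive adverse event listing.

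**What to change.** In item 40 of the follow-up form, insert 'or worsening' after 'new', matching items 39 and 41. In item 51, delete the reference to item numbers, so that it asks openly about any other new or worsening behaviour problem. For consistency, items 5, 8 and 12 may take the same two words, although item 35 already gives them an outlet.

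The cost is a few words on one form, IRB review of the change under Section 12.3, and perhaps a few more yes answers to follow up. No visit, staffing or analysis changes. If any follow-up forms have already been completed, record which wording each child was given, because worsening missed under the present wording may not be recoverable.
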